12. DESCRIPTIVE FACTORS

- Category of MF (see [Appendix B](#)): Primary Myelofibrosis vs. Post ET Myelofibrosis vs. Post PV Myelofibrosis vs. blast-phase MF vs MDS/MPN or MDS
- DIPSS-plus risk (see [Appendix A](#)): High-risk MF vs. Intermediate-2 risk MF

13. TREATMENT/FOLLOW-UP DECISION AT EVALUATION OF PATIENT

Patients who are CR, PR, CI, or SD will continue treatment per protocol.

Patients will be discontinued from treatment and go to event-monitoring phase per Section 4 for any of the following reasons:

- Disease progression (Except relapse that occurs during dose interruption).
- Leukemic transformation (as per WHO criteria)
- Any clinical adverse event, laboratory abnormality, intercurrent illness or other medical condition or situation which occurs such that continued participation in the study would not be in the best interest of the participant
- Hepatotoxicity criteria for treatment discontinuation (see Section [8.2.1](#))
- Pregnancy
- Diagnosis of positive status for HIV or hepatitis B or C
- Continued failure to comply with study procedures or use of the drug as specified in the study protocol such that continued participation in the study would not be in the best interest of the participant
- Withdrawal of consent
- Initiation of non-protocol therapies
- Administrative decision by investigator or sponsor

A patient is deemed *ineligible* if after registration, it is determined that at the time of registration, the patient did not satisfy each and every eligibility criteria for study entry. The patient may continue treatment off-protocol at the discretion of the physician as long as there are no safety concerns, and the patient was properly registered. The patient will go directly to the event-monitoring phase of the study.

- If the patient received treatment, all data up until the point of confirmation of ineligibility must be submitted. Event monitoring will be required per Section 4 of the protocol.
- If the patient never received treatment, on-study material and the End of Active Treatment/Cancel Notification Form must be submitted. No further data submission is necessary.

A patient is deemed a *major violation*, if protocol requirements regarding treatment in Cycle 1 of the initial therapy are severely violated that evaluability for primary end point is questionable. All data up until the point of confirmation of a major violation must be submitted. The patient will go directly to the event-monitoring phase of the study. The patient may continue treatment off-protocol at the discretion of the physician as long as there are no safety concerns, and the patient was properly registered. Event monitoring will be required per Section 4 of the protocol.

A patient is deemed a *cancel* if he/she is removed from the study for any reason before any study treatment is given. On-study material and the End of Active Treatment/Cancel Notification Form must be submitted. No further data submission is necessary.

14. BODY FLUID BIOSPECIMENS

Peripheral blood will be obtained according to IRB-approved collect and store protocol #11-005599 and #12-003574 (PI, [REDACTED]).

15. DRUG INFORMATION

15.1. Imetelstat (GRN163L)

15.1.1. Background

Imetelstat is a potent specific inhibitor of telomerase and is currently in development as a potential therapeutic agent for the treatment of solid tumor and hematological malignancies. Imetelstat has also shown additive and synergistic effects in multiple in vitro and in vivo tumor models when combined with approved anticancer agents, supporting clinical investigation of imetelstat in combination with approved anticancer therapies to potentially improve clinical responses. Additionally, imetelstat is a potent and effective inhibitor of cancer stem cells in vitro and in vivo, suggesting that imetelstat may improve the durability of clinical responses in cancers that have a stem cell component contributing to their maintenance and progression.

[REDACTED]
[REDACTED]
[REDACTED]

A series of black rectangular bars of varying lengths and positions, suggesting a redacted list or table. The bars are arranged vertically and overlap each other, with some being longer and positioned higher than others. The overall effect is a redacted or obscured list of items.

15.1.4. Administration

Administer imetelstat at a constant rate over 2 hours using a programmable volumetric infusion pump. In-line filters may be used but are not required.

Imetelstat will be administered as a 2-hour IV infusion (\pm 10 minutes). The baseline weight will be used to calculate the dose of imetelstat. The dose should be recalculated if there is a \geq 10% weight change from baseline. All patients must be pre-medicated prior to imetelstat administration (see Section 7 for details). Patients require regular monitoring for hematologic toxicity.

15.1.5. Pharmacokinetic information:

a. Absorption – There was a measurable level of imetelstat in a post-treatment bone marrow sample collected 1 day after dosing at 6 mg/kg, resulting in a concentration at

24 hrs post-treatment of 5.54 $\mu\text{g}/\text{mL}$. This confirmed the presence of imetelstat in the target tissue, bone marrow, after IV administration to MM patients.

- b. Distribution – V_{dss} ranged from 41/3 to 71.2 mL/kg at doses of 4.8 to 11.7 mg/kg .
- c. Excretion – $T_{1/2}$ following a single-dose ranged from 4 to 5 hours. Similar to other oligonucleotides, imetelstat excretion is probably mainly via the urinary tract following metabolism of the oligonucleotide sequence into smaller fragments. Based on a preliminary population pharmacokinetic analysis of 59 patients who received 2- or 6-hour weekly IV infusions of imetelstat 0.4 to 11.7 mg/kg (30–1155 mg) or 20–240 mg/m^2 (37.4–516 mg), the estimated CL of imetelstat varied by body size (body weight or BSA) and dose. After correcting for body size, the CL at a BSA of 1.86 m^2 was 0.206 L/hr and total CL was 0.84 L/hr at a dose of 9.4 mg/kg (\approx 380 mg/m^2).

15.1.6. Potential Drug Interactions

To date, no known drug interactions have been identified with imetelstat treatment.

15.1.7. Safety Experience

Refer to Section 1.3.4 for safety experience.

For further details, see the Imetelstat Investigator's Brochure.

15.1.8. Drug Procurement

Imetelstat will be provided free of charge to study participants by Janssen Research & Development.

15.1.9. Nursing Guidelines

As drug is early in development, not all side effects can be known at this time. Monitor patients carefully and instruct patient to report any side effects to the treating physician and/or study team immediately.

In Phase I studies cytopenias (thrombocytopenia and neutropenia) were the primary dose-limiting side effects especially when administered with other cytotoxic agents. Monitor CBC w/differential closely. Instruct patients in signs and symptoms of infection and to report any unusual bruising or bleeding to the study team immediately.

Infusion reactions have been seen and are usually mild-moderate in nature. These usually occur shortly after infusion initiation and can occur with subsequent cycles, despite tolerability of previous cycles. Have emergency medications on hand and administer at the physician's discretion (See Section 8.3 and [Appendix E](#)).

Patients may experience prolonged aPTT times. Instruct patients to report any unusually bleeding to study team immediately.

Gastrointestinal side effects (diarrhea, nausea, vomiting, etc.) have been seen (See Section 9). Treat symptomatically and monitor for effectiveness.

Fatigue is common. Instruct patient in energy conserving lifestyle.

16. STATISTICAL CONSIDERATIONS AND METHODOLOGY

Overview: This protocol will assess the efficacy of different schedules of imetelstat in six cohorts of patients with myelofibrosis (including blast-phase disease in Arm D) and one cohort of patients with MDS/MPN or MDS with spliceosome mutations or ring sideroblasts using a phase II study design in each arm independently.

Descriptive statistics will be used to summarize baseline patient characteristics, treatment administration, efficacy, and safety outcomes. Descriptive summaries of discrete data will present the number of patients and the incidence as a frequency and as a percentage. Descriptive summaries of continuous data will present the group mean, standard deviation, median, minimum, maximum, and sample size.

For regulatory reporting purposes, there are two time points for the analyses: (1) the primary analysis 48 weeks after the last patient has been enrolled, and (2) the final analysis after all patients have completed the study. A separate and detailed statistical analysis plan (SAP) developed prior to primary analysis will supersede analyses specified in the protocol. Deviations from the SAP will be noted in the final study report.

Primary Endpoint: The primary endpoint in each arm of this trial is overall response rate. Overall response will be defined as a CI, PR, or CR (for Arms A, B, C, E, and F) according to the IWG-MRT consensus criteria for MF, or as a HI, PR or CR (for Arm G) according to the IWG consensus criteria for MDS, or the achievement of <5% peripheral blood and bone marrow blast % that lasts for at least two months (for Arm D).

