Final Decision Rule: If 4 or fewer successes are observed in the first 25 evaluable patients, we will consider this regimen ineffective in this patient population. If 5 or more successes are observed in the first 25 evaluable patients, we may recommend further testing of this regimen in subsequent studies in this population.

Power and Significance Level: Assuming that the number of successes is binomially distributed, with a significance level of 10%, the probability of declaring that the regimen warrants further studies (i.e., statistical power) under various success proportions can be tabulated as a function of the true success proportion as shown in the table below.

If the true success proportion is...	0.10	0.15	0.20	0.25	0.30
Then the probability of declaring that the regimen is promising and warrants further study is...	0.10	0.32	0.58	0.79	0.91

Over Accrual: If more than the target number of patients are accrued, the additional patients will not be used to evaluate the stopping rule or used in any decision making process. Analyses involving over accrued patients are discussed in Section [16.6](#).

Sample Size: As of Addendum 3, accrual to Arm C will be permanently discontinued. The 11 patients slotted to enroll on Arm C will now be treated per the Arm A or Arm B dose schedule. A total of 34 patients will be accrued between Arms A, B, and C. Accrual will continue per protocol in Arm D and three additional arms (Arms E, F, and G) will be added. A total of 26 evaluable patients (Arms D and G) or 25 evaluable patients (Arms E and F) will be accrued in each of the remaining arms. An additional 3 patients will be accrued in each arm to account for patients who need to be replaced. Therefore, the maximum overall sample size across all arms of the study is now 148 patients.

As of 22Jan2014 study is closed to enrollment with a total of 80 patients enrolled.

Accrual Rate and Study Duration: As of 22Jan2014, all arms have permanently discontinued accrual. The 11 patients slotted to enroll on Arm C will now be treated per the Arm A or Arm B dose schedule.

Other considerations: Adverse events, quality/duration of response, and patterns of treatment failure observed in this study, as well as scientific discoveries or changes in standard care will be taken into account in any decision to terminate the study

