16.2. Analysis Plan

For regulatory reporting purposes, the primary analysis will commence 48 weeks after the last patient has been enrolled, and the final analysis after all patients have completed the study. Analysis of patients with blast-phase MF (Arm D) and those with MDS/MPN or MDS (Arm G) will be performed and presented separately.

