16.4.3. Transfusion-Independence

Transfusion dependency is defined by a history of at least 2 units of red blood cell transfusions in the last month for a hemoglobin level of less than 85 g/L that was not associated with clinically overt bleeding (see IWG-MRT criteria; [Section 11](#)). The proportion of patients achieving transfusion independence during the first 9 cycles of treatment will be estimated by the number of patients who achieve transfusion independence divided by the total number of evaluable patients who were transfusion dependent at baseline. Ninety-five percent Clopper-Pearson exact

binomial confidence intervals for the true proportion of patients who become transfusion independent will be calculated. The same statistical method will be applied to anemia response for Arms A, B, E and F per IWG-MRT for myelofibrosis (Tefferi et al. 2013) and erythroid response for Arm G per IWG response criteria for MDS ([Cheson et al. 2006](#)).

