AMENDMENT HISTORY

Draft: June 30, 2017

ABBREVIATIONS

AE	Adverse Event
CI	Clinical Improvement
CR	Complete Remission
DIPSS	Dynamic International Prognostic Scoring System
DoR	Duration of Response
ECOG	Eastern Cooperative Oncology Group
eCRF	Electronic Case Report Form
ET MF	Essential Thrombocythemia Myelofibrosis
HI	Hematological Improvement
IV	Intravenous
IWG-MRT	International Working Group for Myeloproliferative Neoplasms Research and Treatment
MDS	Myelodysplastic Syndromes
MedDRA	Medical Dictionary for Regulatory Activities
MF	Myelofibrosis
MPN	Myeloproliferative Neoplasm
NCI CTCAE	National Cancer Institute Common Terminology Criteria for Adverse Events
OS	Overall Survival
PMF	Primary Myelofibrosis
PR	Partial Remission
PV	Polycythemia Vera
SAP	Statistical Analysis Plan
SD	Standard Deviation
SMQs	Standardized MedDRA Queries
WBC	White Blood Cell

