4.3.2. Analysis Methods

Subjects' status of spleen response and transfusion-independence will be listed for all eligible subjects.

Duration of response will be estimated using the Kaplan-Meier method. Approximate 95% confidence intervals for median duration of response will be computed using the formula proposed by Brookmeyer and Crowley. The same method will be applied for OS.

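### SAP 4.3 has no separate anemia or erythroid response rate and only lists spleen response and transfusion independence, though the protocol planned exact intervals for all four; covered durations and data cut are also unstated

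*Protocol*

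**What the plan says.** **Authority and timing.** Protocol section 16 sets two analysis times for regulatory reporting: "the primary analysis 48 weeks after the last patient has been enrolled, and (2) the final analysis after all patients have completed the study". Section 16.2 repeats the first. Section 16.1 adds: "As of 22Jan2014 study is closed to enrollment with a total of 80 patients enrolled". Section 16 also says of the SAP: "A separate and detailed statistical analysis plan (SAP) developed prior to primary analysis will supersede analyses specified in the protocol". The SAP amendment history has one entry: "Draft: June 30, 2017".

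**Protocol analyses.** Section 16.4.2 plans a spleen response proportion with a 95% Clopper-Pearson interval. Section 16.4.3 does the same for transfusion independence: "binomial confidence intervals for the true proportion of patients who become transfusion independent will be calculated". It then extends the method: "The same statistical method will be applied to anemia response for Arms A, B, E and F", and to erythroid response in Arm G. Section 16.4.4 plans Kaplan-Meier durations for overall, hepatosplenic and anemia response, and for erythroid response in Arm G.

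**SAP analyses.** SAP 1.1 repeats the protocol's secondary objectives, including spleen size, anemia or transfusion independence, and onset and durability. SAP 4.3.1 defines spleen response, transfusion independence, time to response, duration of response and overall survival. For the first two, SAP 4.3.2 says that subjects' "status of spleen response and transfusion-independence will be listed for all eligible subjects".

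**The concern.** An SAP that replaces the protocol's analyses has to carry every estimate the trial still intends to report. This one keeps the objectives but not the estimators that answer them. Followed as written, the report could show line listings for spleen response and transfusion independence, nothing separate on anemia or erythroid response, and no interval for any of them. A reader would have to count responders and choose denominators unaided.

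The date makes this more important. The trial is open-label and single-center, and protocol 1.4.1 describes observed responses and toxicity already leading to changes in the arms. When an SAP is drafted years after the planned primary analysis time, readers need to know what changed, when, and at which data cut the results were taken.

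**Working it through.** No calculated figure in the plan bears on this point. The check is calendar arithmetic plus a comparison of sections.

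**1. Dates.** Inputs: closure of enrolment on 22 January 2014 (protocol 16.1), 48 weeks (16 and 16.2), SAP draft of 30 June 2017 (amendment history).
- 48 × 7 = 336 days; 22 January 2014 + 336 days = 24 December 2014.
- 24 December 2014 to 30 June 2017 = 919 days; 919 / 365.25 = 2.52 years.
- Closure is the latest possible last enrolment, so this is a minimum gap. If the last patient entered 3 or 6 months earlier (an assumption), it is 2.77 or 3.02 years.

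**2. Planned analysis against SAP analysis.**

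| Item | Protocol | SAP |
|---|---|---|
| Spleen response | 16.4.2: proportion, exact 95% CI | 4.3.1 defines; 4.3.2 lists |
| Transfusion independence | 16.4.3: proportion over the first 9 cycles, exact 95% CI | 4.3.1 redefines; 4.3.2 lists |
| Anemia response (A, B, E, F) | 16.4.3: same method | Not defined or analysed separately |
| Erythroid response (G) | 16.4.3: same method | Not defined or analysed separately |
| Durations | 16.4.4: overall, hepatosplenic, anemia, erythroid | Kaplan-Meier for an unspecified response |
| Overall survival | Not among the section 2 goals; survival follow-up in Table 3 | Major secondary endpoint, Kaplan-Meier |
| Data cut | 48 weeks after last enrolment, and final | None stated |

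Four planned secondary rates with exact intervals become none in SAP 4.3.

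**3. Transfusion definitions.** Three are in play.
- *Protocol Table 15, footnote 6.* Dependence is at least 6 units in 12 weeks for hemoglobin below 85 g/L, with the latest transfusion within 28 days. Independence is no transfusion over a rolling 12 weeks, ending with hemoglobin of at least 85 g/L.
- *Protocol 16.4.3.* Dependence is at least 2 units in the last month **for** hemoglobin below 85 g/L.
- *SAP 4.3.1.* Dependence is at least 2 units in the last month **or** baseline hemoglobin below 85 g/L. Independence is at most 1 unit over 30 days or more, or a rise above 2 g/dL without transfusion when baseline is below 85 g/L.

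The SAP thus changes both numerator and denominator. Read literally, an untransfused subject below 85 g/L counts as dependent and then meets the first independence condition without any hemoglobin change.

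**4. Does the SAP hemoglobin criterion replace anemia response?** Only in part. Table 15 applies the hemoglobin criterion for anemia response to baselines below 100 g/L, and Table 17 applies erythroid response to baselines below 11 g/dL (110 g/L). The SAP criterion stops at 85 g/L. Untransfused subjects from 85 to below 100 g/L (MF arms), or to below 110 g/L (Arm G), have no separate anemia endpoint.

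**5. What the restored intervals would look like.** The documents give no denominators, so these are assumed. The Clopper-Pearson limits are the 2.5% quantile of Beta(x, n−x+1) and the 97.5% quantile of Beta(x+1, n−x).
- 0/10: 0% to 30.8%
- 3/10: 6.7% to 65.2%
- 6/20: 11.9% to 54.3%

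**The case against.** The best case for the SAP has five parts.

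- **Anemia still counts.** Anemia response is one route to clinical improvement and erythroid response one route to hematologic improvement, so both feed the primary endpoint. The SAP's transfusion independence also has a hemoglobin route. This is correct, and it rules out saying that anemia goes wholly unmeasured. Neither route gives a separate rate.
- **A general rule supplies percentages.** SAP section 2 summarises categorical variables by frequency and percentage in general, so a bare transfusion-independence or spleen percentage is arguable. But 4.3.2 specifically calls for a listing, and the exact interval is missing either way.
- **Durability may be intact.** SAP 1.1 keeps durability for primary and secondary endpoints, and 4.3.1 does not restrict duration to overall response. It is therefore wrong to say that the component durations were removed; the text is ambiguous. The ambiguity matters because the SAP's events are progression, or relapse for complete responders, whereas Table 15 also counts loss of anemia or spleen response as relapse.
- **Silence does not cancel the 48-week analysis.** The SAP may serve the final analysis. Nine 28-day cycles are 252 days, or 36 weeks, so without delays or interruptions the last patient's core-phase assessments precede 48 weeks. This weakens any claim of a large effect on the response rate. The cut still needs stating, because protocol 8.1 allows efficacy evaluation in the extension phase.
- **The stakes are modest.** Eighty patients are spread over several arms, Arms A to C are described as a pilot with mainly descriptive reporting, and overall survival has no planned test. This stands, and it limits severity.

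A reader might also infer that endpoints were dropped or added because the results were known. The documents do not support that. They give one draft date and do not say when data were accessed, whether a 48-week analysis was run, or whether another SAP version exists.

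**Conclusion.** The point holds as a gap between the SAP's stated objectives and its analyses. All four secondary response rates lose their planned exact intervals. Two of them, anemia and erythroid response, lose any separate rate, and the other two become listings. The coverage of duration of response is unclear, no data cut is stated, and the transfusion definitions conflict.

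The timing is secondary but should be disclosed. The gap of at least 2.5 years rests on the closure date and on the listed draft being the only SAP. The supersession clause describes an SAP developed before the primary analysis. If a 48-week analysis was run before this draft, the SAP does not meet that description; if none was run, the planned time passed without comment. The documents do not say which.

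The change should be made, but nothing here invalidates the primary endpoint analysis, and no finding of intentional selective reporting is warranted.

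**What to change.** 1. In SAP 4.3, report spleen response, transfusion independence, anemia response (Arms A, B, E, F) and erythroid response (Arm G) as n/N with a 95% Clopper-Pearson interval by arm, and state each denominator.
2. Reconcile the transfusion dependence and independence definitions in protocol Table 15, protocol 16.4.3 and SAP 4.3.1, and state which is analysed and over what period.
3. Name each protocol 16.4.4 duration that will be estimated, with the event that ends it.
4. In SAP 4.2.2, state the data cut and separate results at the 48-week point from those of the final analysis.
5. State the SAP's date relative to the planned primary analysis and to data access. Label overall survival and the changed definitions as added or changed after the protocol. If an analysis is deliberately omitted, record and justify that.

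The cost is SAP wording and a few tables. Hemoglobin, transfusion and spleen assessments are already in protocol Table 3, and SAP 4.2.2 already uses the interval method. Intervals in small arms will be wide, and some results will carry a post hoc label.
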